### **2.2. Study Participants**

Patients meeting inclusion and exclusion criteria at Stanford University Medical Center or Santa Clara Valley Medical Center (SCVMC) will be eligible to participate in the study. Study procedures will be conducted at Stanford University Medical Center and SCVMC. All standard-of-care (SOC) procedures will be conducted at the respective sites. However, the final 6-month study visit will be conducted at Stanford for all participants irrespective of whether they were enrolled at Stanford or SCVMC.

#### **Inclusion Criteria**

1. Age  $\geq$ 18 years
2. Receiving or planning to receive maintenance hemodialysis
3. Candidate for arteriovenous fistula
4. Ability to sign informed consent

5. At least 3 mm venous diameter within recipient vein

#### Exclusion Criteria

1. History of stroke, transient ischemic attack or intracranial hemorrhage
2. History of or high level of suspicion for severe arterial insufficiency of the hand
3. Indication or ongoing therapy with other antiplatelet agents, other than aspirin 81 mg daily
4. Indication or ongoing therapy with anticoagulants, including warfarin, low molecular weight heparin, factor Xa inhibitors or direct thrombin and other inhibitors
5. Indication or ongoing therapy with strong inhibitors or strong inducers of CYP3A

Study participants will be followed up at approximately 6 weeks, 3 months, 4 months and 6 months after randomization. At each of these visits, data will be collected on the following measures:

- Patency of fistula (yes/no)
- Fistula being used for dialysis at least 6 times in 3 weeks (yes/no)
- Adverse events
- Additional procedures performed to aid in fistula maturation (yes/no)
  - Type of procedure
  - Successful (yes/no)
- BARC and GUSTO Bleeding Classification

In addition, at the 6 week and 6 month follow up visits, data will be collected on:

- Diameter of fistula by ultrasound
- Velocity of fistula by ultrasound

### 2.3. Study Endpoints

The primary efficacy outcome is time to AV fistula functional maturation (defined as successful cannulation of the AV fistula for six hemodialysis sessions within three weeks).

The secondary efficacy outcomes are:

- AV fistula use within 180 days of surgery
- AV fistula patency at 150-180 days, with at least 50% increase in vein diameter by ultrasound compared with preoperative vein diameter measurement
- Update: New secondary outcome added: AV fistula functional or anatomic maturation at 180 days as determined by the PI

The safety outcomes are bleeding events as determined by BARC and GUSTO criteria.

BARC Bleeding Classification

- Type 0: No bleeding

- Type 1: Bleeding that is not actionable and does not cause the patient to seek unscheduled performance of studies, hospitalization, or treatment by a healthcare professional; may include episodes leading to self-discontinuation of medical therapy by the patient without consulting a healthcare professional
- Type 2: Any overt, actionable sign of hemorrhage (e.g., more bleeding than would be expected for a clinical circumstance, including bleeding found by imaging alone) that does not fit the criteria for type 3, 4, or 5 but does meet at least one of the following criteria: (1) requiring nonsurgical, medical intervention by a healthcare professional, (2) leading to hospitalization or increased level of care, or (3) prompting evaluation
- Type 3
  - Type 3a: Overt bleeding plus hemoglobin drop of 3 to 5 g/dL\* (provided hemoglobin drop is related to bleed) Any transfusion with overt bleeding
  - Type 3b: Overt bleeding plus hemoglobin drop >5 g/dL\* (provided hemoglobin drop is related to bleed); Cardiac tamponade; Bleeding requiring surgical intervention for control (excluding dental/nasal/skin/hemorrhoid); Bleeding requiring intravenous vasoactive agents
  - Type 3c: Intracranial hemorrhage (does not include micro-bleeds or hemorrhagic transformation, does include intraspinal); Subcategories confirmed by autopsy or imaging or lumbar puncture; Intraocular bleed compromising vision
- Type 4 CABG bleeding
- Type 5: Fatal bleeding

#### GUSTO Bleeding Classification

- Severe: Bleeding\* that was fatal, intracranial, or that caused hemodynamic compromise requiring intervention (e.g., systolic blood pressure <90 mm Hg that required blood or fluid replacement, or vasopressor/inotropic support,\*\* or surgical intervention).
- Moderate: Bleeding\* requiring transfusion of whole blood or packed red blood cells without hemodynamic compromise (as defined above).
- Mild: Bleeding\*: Bleeding without blood transfusion or hemodynamic compromise.

\*In all cases, bleeding must be clinically overt.

\*\*Need for vasopressor/inotropic support for hemodynamic compromise, even if blood pressure

### **3. Statistical Analysis**

#### **3.1. Data monitoring and quality**

We will perform periodic data quality checks for missing data using reports generated in REDCap where data are being collected. After 4 patients have completed follow-up we will review the data for completeness and value checks. Thereafter, we will conduct two additional data quality checks: after an additional 10 and 30 patients have completed follow-up.

Ongoing data monitoring will be conducted by the monitoring coordinator at SCCR to ensure compliance.

#### **3.2. Handling of Missing Data**

We anticipate minimal missing data in this study. We expect that a small proportion of subjects randomized for the study (1-2 subjects) will not complete all visits. We will fully describe missing data for each variable and any pertinent patterns of missingness (e.g. how missingness is related to specific baseline measurements or time, if at all). The statistical methods we will use are particularly flexible for missing data and allow for systematic missingness that is related to observed features.

#### **3.3. Descriptive Statistics**

We will provide descriptive statistics such as means, medians, standard deviations and interquartile ranges for continuous measurements, and frequency statistics for categorical characteristics. We will use graphical tools such as histograms and boxplots to assess distributional aspects of continuous variables.

#### **3.4. Statistical Analysis:**

We will derive cumulative incidence plots to depict time to fistula use, stratified by treatment arm and fistula location.

The primary outcome is time to AV fistula maturation, defined as successful cannulation of the AV fistula for six hemodialysis sessions within three weeks.

Subjects who are lost to follow up or who die prior to maturation will be censored at the time of death or last recorded activity.

Our primary analysis will be based on the intention-to-treat principle. To that end, patients will be analyzed according to their randomized treatment assignment, and all patients randomized to treatment assignment will be included in the analysis even if they are lost to follow up or die before the end of their observation period. We will use a log-rank test stratified by location of fistula to assess whether time to maturation of AV fistula differs between treatment arms (vorapaxar versus placebo). The test will be two-sided and conducted at the 0.05 level of significance.

A Cox proportional hazards regression model of treatment arm and other characteristics of interest (if required) will be employed secondarily to estimate an adjusted treatment effect.

Other secondary analyses involve the use of logistic regression techniques to evaluate the effect of treatment on secondary endpoints – use of AV fistula within 180 days, AV fistula patency within 150-180 days and AV fistula functional or anatomic maturation at 180 days as determined by the PI. We will also compare rates of bleeding by treatment arm using t-tests or Wilcoxon rank sum tests as appropriate.

**UPDATED: Based on low enrollment and early termination of the study, the planned analysis as described above will not be conducted. Instead, we will conduct a descriptive analysis only.**

**UPDATED: The secondary outcome “AV fistula functional or anatomic maturation at 180 days as determined by the PI” will be defined using clinically adjudicated after a review of the medical record.**

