## 1. Introduction

### 1.1. Background

End-stage renal disease affects nearly 500,000 persons in the US and more than 2 million persons worldwide. In the US and most developed countries, hemodialysis is the predominant dialytic modality. While effective at sustaining life for most patients, hemodialysis rarely restores health. Roughly one in five patients on dialysis die each year; patients who survive experience poor functional status, impaired physical and cognitive function and severely impaired health-related quality of life. Moreover, the cost of the ESRD program exceeds \$40B in the US annually (1).

Hemodialysis vascular access is often referred to as the "Achilles Heel" of dialysis care. The Brescia-Cimino (radiocephalic end-to-side) fistula is considered to be the gold standard vascular access (2); upper arm arteriovenous fistulae are often created instead.

Polytetrafluoroethylene (PTFE) grafts are next best, but are frequently complicated by graft "thrombosis," commonly caused not by hematologic abnormalities, but rather by intimal hyperplasia at the venous anastomosis. Unfortunately, the majority of patients have insufficient time to undergo pre-emptive creation of an arteriovenous fistula or graft, and most patients start hemodialysis with either a temporary or "semi-permanent" tunneled catheter, often placed in one of the internal jugular veins.

For patients who do undergo fistula creation, either in advance of (optimally) or after starting hemodialysis, a sizeable fraction of arteriovenous fistulae never matures sufficiently to be usable for hemodialysis. It is common for patients to undergo three or more attempts at fistula creation, extending the time during which they experience a heightened risk of infection and venous stenosis/thrombosis of the internal jugular veins or in some cases other complications including superior vena cava syndrome. Therapeutic agents that could facilitate maturation of arteriovenous fistulae could vastly improve the health and well-being of patients on hemodialysis, and could well result in enhanced survival.

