#### **Power/Sample Size**

We have sufficient power to address our primary aim. Based upon a sample size of n=25 patients per group for this pilot study, we have approximately 70% power to detect a hazard ratio of 2.05 between treatment arms, assuming that only 50% of subjects will experience maturation by six months post randomization in the placebo group. If only 40% of subjects experience maturation by six months post randomization we have over 70% power to detect a hazard ratio of 2.15.

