Hospitalization					
Unstable angina					
Myocardial infarction					
Cardiac catheterization					
PCI					
CABG					
Non-coronary vascularization					
Stroke					
TIA					
Transfusion					

Figure 1. Kaplan-Meier plot of time to fistula maturation by treatment arm and location of fistula

Figure 2. All outcomes with forest plot for point estimate and 95% confidence interval

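### Cumulative incidence in SAP 3.4, Kaplan-Meier in the Figure 1 shell, deaths censored: drawn that way, the curve would slightly overstate the share of patients who mature

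*SAP*

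**What the plan says.** SAP section 3.4 describes the curves this way: "We will derive cumulative incidence plots to depict time to fistula use, stratified by treatment arm and fistula location". Protocol section 2.7 makes the same promise. In SAP Appendix 1 the shell for Figure 1 reads: "Kaplan-Meier plot of time to fistula maturation by treatment arm and location of fistula". The two descriptions differ in the estimator and in the name of the event.

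On deaths, section 3.4 says: "Subjects who are lost to follow up or who die prior to maturation will be censored at the time of death", or else at the last activity on record. Protocol 2.7 has the same rule. Neither document mentions competing risks or names an estimator that allows for them.

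Three other statements bear on the size of the problem:

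- SAP 1.1, on background mortality: "Roughly one in five patients on dialysis die each year".
- SAP 3.2, on incomplete follow-up: "We expect that a small proportion of subjects randomized for the study (1-2 subjects) will not complete all visits".
- The SAP power section, which works "assuming that only 50% of subjects will experience maturation by six months post randomization in the placebo group" with a hazard ratio of 2.05, or alternatively 40% with a hazard ratio of 2.15.

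An update at the end of SAP 3.4 withdraws the analysis set out above it and substitutes a descriptive one, because of low enrolment and early termination. It does not say whether the curves or Figure 1 remain. The figure shell is still in Appendix 1.

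**The concern.** Death before maturation rules the event out. It does not merely hide it, as loss to follow-up does. One minus a Kaplan-Meier curve with deaths censored estimates the share who would mature if nobody died, because it assumes that the dead would have gone on to mature at the survivors' rate. Cumulative incidence with death as a competing event estimates the share who actually mature. The two differ only because of deaths, so the choice between the wording of section 3.4 and the wording of the shell changes the plotted number.

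This matters more in a descriptive report. Without a test or a hazard ratio, a reader will take the height of the curve as an absolute proportion, and that is the one use for which censoring deaths is unsuitable. The event name also needs settling. SAP 2.3 lists fistula use within 180 days as a secondary outcome separate from time to functional maturation, so a curve of use is not clearly a curve of the primary outcome.

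**Working it through.** The documents give no figure for this difference, so there is none to reproduce. The power statement supplies the maturation inputs only; its power values play no part here.

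**Inputs**

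- Maturation by 6 months on placebo, p: 50% or 40% (SAP power section).
- Hazard ratios: 2.05 with 50%, 2.15 with 40% (same section). On vorapaxar, 1 − 0.5^2.05 = 75.9% and 1 − 0.6^2.15 = 66.7%.
- Death by 6 months, d, in four cases:
  - 20% per year (SAP 1.1): 1 − 0.8^0.5 = 10.6%.
  - 10% per year (assumption): 1 − 0.9^0.5 = 5.1%.
  - One of 50 dies (SAP 3.2, if the only non-completer dies): 2%.
  - Two of 50 die (SAP 3.2, if both non-completers die): 4%.
- Assumptions: constant, independent hazards for maturation and death, and equal mortality in the two arms.

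**Formulas**, with the half-year as the time unit, λ = −ln(1 − p) and μ = −ln(1 − d):

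- Deaths censored: 1 − KM = 1 − exp(−λ) = p.
- Death competing: CIF = λ/(λ + μ) × [1 − exp(−(λ + μ))].

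**Worked case, 20% per year**, μ = 0.1116:

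- Placebo, λ = 0.6931: CIF = 0.6931/0.8047 × (1 − 0.4472) = 0.476. Excess 50.0 − 47.6 = 2.4 points.
- Vorapaxar, λ = 2.05 × 0.6931 = 1.4209: CIF = 1.4209/1.5325 × (1 − 0.2160) = 0.727. Excess 75.9 − 72.7 = 3.2 points.

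**All cases** (excess of 1 − KM over CIF at 6 months, in points):

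| 1 − KM | CIF at 20%/year | Excess, 20%/year | Excess, 10%/year | Excess, 2 of 50 die | Excess, 1 of 50 dies |
|---|---|---|---|---|---|
| 40.0% (placebo) | 38.0% | 1.97 | 0.95 | 0.74 | 0.37 |
| 50.0% (placebo) | 47.6% | 2.39 | 1.15 | 0.89 | 0.44 |
| 66.7% (HR 2.15) | 63.7% | 2.95 | 1.42 | 1.10 | 0.55 |
| 75.9% (HR 2.05) | 72.7% | 3.16 | 1.52 | 1.18 | 0.59 |

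**Sensitivity**

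- Treating the design proportions as the competing-risk values instead moves no entry in the 20% and 10% columns by more than 0.1 point.
- If no fistula matured in the first 6 to 12 weeks (assumption), the excess at 20% per year would be 2.5 to 5.5 points. Constant hazards are therefore not the worst case.

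**Effect on the contrast.** At 50% and hazard ratio 2.05, the difference between arms is inflated by 3.16 − 2.39 = 0.77 points at 20% per year and by 1.52 − 1.15 = 0.37 at 10%. With no treatment effect and equal mortality it is not inflated at all.

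**Scale.** With 25 per arm, one patient is 4 points and the standard error of 50% is √(0.25/25) = 10 points. For a curve of about 12 patients (an arm split evenly by location, an assumption), it is √(0.25/12) = 14 points.

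**The case against.** The strongest reply is that the update in section 3.4 may have removed the problem. The curve sentence and the censoring rule both stand above a statement that the analysis so described will not be conducted. The surviving shells prove little, since Appendix 1 also keeps hazard-ratio and odds-ratio columns and a forest plot. That stands: a reader might infer that the report will carry a biased curve, but the documents support only a conditional statement.

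The estimator is also partly inferred. Section 3.4 says cumulative incidence, which is the right quantity, and its censoring rule leads into the log-rank test, where it is a valid cause-specific rule. Only the Figure 1 shell names Kaplan-Meier. The event names may likewise mean the same thing, since the item collected at each visit is use at least six times in three weeks. These points reduce the fault to an unresolved conflict, but they do not resolve it.

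Three stronger readings are not supported:

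- **That the log-rank test or Cox model is invalid.** Censoring at death is legitimate for comparing cause-specific hazards.
- **That Figure 1 will contradict Table 3.** The maturation row in Table 3 is time in days. It has no 6-month maturation percentage, and the nearest percentage row is use within 180 days.
- **That SAP 3.2 must be restated because 50 × (1 − 0.8^0.5) = 5.3 deaths would be expected.** The one-in-five figure is background for patients on dialysis and is not a design assumption. The trial also admits patients only planning dialysis and excludes some higher-risk histories such as stroke. A forecast for 50 patients no longer applies to a trial that stopped early.

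**Conclusion.** The concern holds as a conditional and minor point. Section 3.4 and the Figure 1 shell conflict on estimator and event name, and the only stated rule for deaths is censoring. If the figure is drawn as Kaplan-Meier with deaths censored, it would overstate the share of patients who mature by 6 months. The size is about 2 to 3 points at the background mortality, 1 to 1.5 points at an assumed 10% per year, and 0.4 to 1.2 points if deaths are limited to the non-completers in SAP 3.2.

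These figures rest on constant independent hazards, equal mortality in the arms and the design's maturation rates. They describe the planned trial of 25 per arm, not the smaller one that was run. The excess is well within sampling error and would not change a conclusion about treatment. The reason to act is that the curve would carry a label it does not earn, and the correction is easy.

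**What to change.** In SAP 3.4 and in the Figure 1 shell, use the same event name, functional maturation as defined for the primary outcome, and the same estimator: Aalen-Johansen cumulative incidence with death as a competing event, by arm and fistula location, with the number of deaths shown for each curve. Limit the rule that censors at death to cause-specific hazard comparisons (log-rank test, Cox model). Add to the descriptive-only update a sentence stating that this version of Figure 1 is kept.

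The cost is a few lines of SAP wording and a small programming change in either software package that the SAP names. No new data are needed, because the censoring rule already requires dates of death. The log-rank test and Cox model, as written, would not change.

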#### ***Preliminary Data***

Numerous small studies have attempted to improve short- and longer-term function of arteriovenous fistulae and grafts with a variety of therapeutic agents, including warfarin, aspirin, fish oil, dipyridamole and several newer antiplatelet agents, including ticlopidine and more recently clopidogrel (3-7). In order to address the pressing need for improved outcomes, the National Institutes of Health (NIH) National Institutes of Diabetes and Digestive and Kidney Diseases (NIDDK) assembled the “Dialysis Access Consortium” more than 10 years ago – a consortium of highly qualified investigators whose aim was to design two major clinical trials to address failure of arteriovenous fistulae and grafts, respectively (8). [name] served on the Data Safety and Monitoring Board for both of the DAC trials.

The DAC investigators conducted a randomized, placebo-controlled trial of clopidogrel in patients receiving arteriovenous fistulae (9) (another trial examining arteriovenous grafts will not be discussed here). Interestingly, clopidogrel was shown to enhance short-term patency of arteriovenous fistulae, but failed to result in improved maturation, sufficient for the fistula to be consistently used for maintenance hemodialysis. Roughly six of 10 patients assigned to the trial (all at outstanding clinical centers) failed to have a usable fistula at 3-4 months, highlighting the need for more effective therapy. Despite the DAC fistula study having been stopped prematurely for “efficacy” (on the primary outcome of early fistula patency), few patients receive clopidogrel for this purpose in clinical practice.

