	
**Need for vasopressor/inotropic support for hemodynamic compromise, even if blood pressure
 
Statistical Methods:
 
Descriptive statistics such as means, medians, standard deviations and interquartile ranges will be presented for continuous measurements, and frequency statistics will be presented for categorical characteristics. Graphical tools such as histograms and boxplots will be used to assess distributional aspects of continuous variables.
 
Cumulative incidence plots will be derived to depict time to fistula use, stratified by treatment arm and fistula location.
 
The primary outcome is time to AV fistula maturation, defined as successful cannulation of the AV fistula for six hemodialysis sessions within three weeks.
 
Subjects who are lost to follow up or who die prior to maturation will be censored at the time of death or last recorded activity.
 
Our primary analysis will be based on the intention-to-treat principle. To that end, patients will be analyzed according to their randomized treatment assignment, and all patients randomized to treatment assignment will be included in the analysis even if they are lost to follow up or die before the end of their observation period. We will use a log-rank test stratified by location of fistula to assess whether time to maturation of AV fistula differs between treatment arms (vorapaxar versus placebo). The test will be two-sided and conducted at the 0.05 level of significance.
 
A Cox proportional hazards regression model of treatment arm and other covariates of interest will be employed secondarily to estimate an adjusted treatment effect.
 
Other secondary analyses involve the use of logistic regression techniques to evaluate the effect of treatment on secondary endpoints – use of AV fistula within 180 days and AV fistula patency within 150-180 days.
 
Power/Sample Size:
 
We have sufficient power to address our primary aim. Based upon a sample size of n=25 patients per group for this pilot study, we have approximately 70% power to detect a hazard ratio of 2.05 between treatment arms, assuming that only 50% of subjects will experience maturation by six months post randomization in the placebo group. If only 40% of subjects experience maturation by six months post randomization we have over 70% power to detect a hazard ratio of 2.15.

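### The primary-outcome censoring rule removes patients whose fistula is already recorded as lost, so any retained Kaplan-Meier curve overstates maturation in an arm that has such patients

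*SAP*

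**What the plan says.** The primary outcome in SAP 3.4 is "time to AV fistula maturation, defined as successful cannulation of the AV fistula for six hemodialysis sessions within three weeks". The censoring rule is one sentence, which begins "Subjects who are lost to follow up or who die prior to maturation will be censored" and sets the date at death or the last activity on record. Protocol 2.7 (Statistical Methods) has the same rule: such patients "will be censored at the time of death or last recorded activity". Neither document makes fistula loss an endpoint state, a competing event or an exception to censoring.

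The primary test was planned as follows: "We will use a log-rank test stratified by location of fistula to assess whether time to maturation of AV fistula differs between treatment arms". Fistula location is its only stratification factor.

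Four other parts of the plan bear on the point:

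- SAP 2.2 and protocol 2.5 collect patency (yes/no), fistula use, and any procedure to aid maturation with its success, at 6 weeks, 3 months, 4 months and 6 months.
- SAP 3.2 expects 1-2 randomized subjects not to complete all visits. It says the methods can accommodate missingness related to observed features.
- SAP 3.4 names cumulative incidence plots, but Figure 1 in the appendix is a Kaplan-Meier plot. No competing-risk estimator is specified.
- An update at the end of SAP 3.4 withdraws the planned analysis after low enrollment and early termination, and substitutes a descriptive one. The appendix still lists Figure 1, and a time-to-maturation row in Table 3.

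**The concern.** Kaplan-Meier and the log-rank test assume that a censored patient would have gone on to mature at the same rate as those still followed. For a patient whose fistula is recorded as lost and not restored, the trial already knows otherwise. Two patients with the same fistula outcome are therefore scored differently according to whether they kept attending.

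The assurance in SAP 3.2 does not cover this. Recorded patency is an observed feature closely tied to maturation, but the log-rank test does not use it and the Cox model names no specific covariates.

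The number of such patients could differ by arm. Hypothesis 2 predicts better patency on vorapaxar, and protocol 2.2 reports of an earlier trial that "clopidogrel was shown to enhance short-term patency of arteriovenous fistulae, but failed to result in improved maturation". In a descriptive report without a test, the plotted curve is itself the result, so it should not depend on attendance after failure.

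**Working it through.** **Inputs from the documents.** 25 patients per arm; placebo maturation at six months 50%, or 40% in the second scenario; hazard ratio 2.05 (SAP, Power/Sample Size); 1-2 non-completers (SAP 3.2). The plan gives no figure for the effect of its censoring rule, so there is none to reproduce. It also gives no rate of fistula loss or of drop-out after loss; those used below are assumptions.

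**Upper bound: drop-out before any maturation.** In an arm of n with true maturation share p and k lost-fistula patients censored early, 1 − KM at six months = p·n/(n − k).

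| True p | k = 1 | k = 2 | k = 5 |
|---|---|---|---|
| 50% | 12.5/24 = 52.1% (+2.1) | 12.5/23 = 54.3% (+4.3) | 12.5/20 = 62.5% (+12.5) |
| 40% | 10/24 = 41.7% (+1.7) | 10/23 = 43.5% (+3.5) | 10/20 = 50.0% (+10.0) |

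The k = 5 column is beyond what SAP 3.2 expects. If half the maturations come before the drop-out, k = 1 and k = 2 give +1.4 and +3.0 points at 50%, and +1.1 and +2.2 at 40%.

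**Late drop-out: after the 4-month call, about day 122.** Assume a constant maturation hazard with p = 50% at day 180.

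- Not matured at day 122: 0.5^(122/180) = 62.5%.
- Maturing between day 122 and day 180: 62.5% − 50% = 12.5%.
- k = 1 (4% of the arm): KM = 0.625 × [1 − 0.125/(0.625 − 0.04)] = 0.491, an overstatement of 0.9 points.
- k = 2 (8%): KM = 0.625 × [1 − 0.125/(0.625 − 0.08)] = 0.482, an overstatement of 1.8 points.

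**Dependence on the maturation share.** The upper bound equals p·k/(n − k), so it rises with p. A hazard ratio of 2.05 implies 1 − 0.5^2.05 = 75.9% maturation on vorapaxar. There the early-drop-out bound is 0.759/24 = 3.2 points for k = 1 and 0.759 × 2/23 = 6.6 points for k = 2.

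**Effect on the comparison.** The true difference is 75.9 − 50.0 = 25.9 points. If both non-completers are early lost-fistula placebo patients, it becomes 75.9 − 54.3 = about 21.5. If both are on vorapaxar, it becomes 82.4 − 50.0 = 32.4. The distortion can go either way.

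**Larger drop-out, by simulation.** Assumed: 200,000 patients per arm, fistula loss 30% on placebo and 10% on vorapaxar, true hazard ratio about 2.05.

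| Drop-out after loss (placebo / vorapaxar) | 1 − KM (placebo / vorapaxar) | Hazard ratio |
|---|---|---|
| 25% / 25% | 53.1% / 77.6% | 1.96 |
| 50% / 50% | 57.6% / 79.4% | 1.84 |
| 100% / 100% | 68.7% / 83.6% | 1.61 |
| 10% / 80% | 51.4% / 81.9% | 2.30 |

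The first row already implies 25 × (0.30 × 0.25 + 0.10 × 0.25) = 2.5 such patients in 50, more than the SAP expects. In the last row the overstatement is larger in the arm that loses fewer fistulas.

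**Smaller arms.** The documents give no final enrollment. If an arm had 10 patients (assumption) and 5 matured, one early lost-fistula censoring would move 50% to 5/9 = 55.6%.

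**The case against.** The strongest reply is that little is left to bias. The tests are withdrawn, SAP 3.2 expects only 1-2 non-completers and promises to describe missingness, and the Kaplan-Meier shell may simply not have been revised. Much of this stands. No confirmatory comparison is affected, and on the SAP's own expectation the effect is a few points. It does not remove the point, because the appendix still lists the curve and the time summary, and no other text says how recorded fistula loss is handled.

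The figure of 1-2 may also be low. Protocol 2.2 says roughly one in five dialysis patients die each year. Applied to 50 patients for six months, that is 50 × (1 − 0.8^0.5) = about 5 deaths. This is only illustrative, since trial patients may be healthier, and only deaths after fistula loss add to this particular bias.

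A second fair objection is that one 'no' for patency need not be final, because the trial records procedures that may restore a fistula. This stands, and the replacement rule has to allow for it.

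A reader might also infer that patients with a lost fistula will skip the last visit, because "the final 6-month study visit will be conducted at Stanford for all participants irrespective of whether they were enrolled at Stanford or SCVMC". That is plausible, but the documents give no evidence for it. Such patients would already have had the 4-month call, so the smaller late-drop-out figures would apply to them.

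**Conclusion.** The point holds in a limited form. The rule censors patients already known to have a lost fistula, and any one-minus-Kaplan-Meier estimate then overstates maturation in an arm that has them. With 25 per arm, 50% maturation and 1-2 non-completers, the overstatement is at most about 2 to 4 points in one arm. The top of that range requires both non-completers to be lost-fistula patients in the same arm who leave before any maturation. If they leave after the 4-month call it is about 1 to 2 points. It is larger with higher maturation, more drop-out or smaller arms.

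Three stronger readings are tempting, and the documents do not support them:

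- *The bias is always greater in the arm that loses more fistulas, and so always works against vorapaxar.* It follows the number both lost and no longer followed, which can be higher in either arm.
- *Maturation is overstated by ten points or more.* In arms of 25 that needs drop-out well above what SAP 3.2 expects.
- *The primary significance test is compromised.* It will not be conducted. What remains is mainly Figure 1 and the time-to-maturation row of Table 3.

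**What to change.** Replace the censoring sentence in SAP 3.4 and protocol 2.7 with:

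> A patient whose last recorded patency status is 'no', with no later procedure recorded as successful, is kept in the risk set as not matured to day 180, including if the patient later dies or is lost to follow-up. Death before maturation with an open fistula is a competing event. All other patients without maturation are censored at the last date on which fistula-use status was recorded.

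Show any retained curves as competing-risk cumulative incidence, in line with the plots already named in SAP 3.4, and change Figure 1 in the appendix to match. The final clause also settles the meaning of last recorded activity, which is undefined and could be read as a date later than the last check of fistula use.

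The cost is one replaced sentence and one figure label, using data already collected. The small downside is that a fistula reopened after the last contact would be counted as not matured. The change should be made before the descriptive curves are produced.
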